3.7.2. Analysis Windows

Subject visits might not occur on protocol-specified days. Therefore, for the purpose of analysis, observations will be assigned to analysis windows.

In general, the baseline value will be the last nonmissing value on or prior to the first dose date of study drug.

HCV RNA, vital signs, and safety laboratory data collected up to the last dose date + 3 days are considered to be on-treatment data and HCV RNA, vital signs and safety laboratory data collected after the last dose date + 3 days are considered posttreatment data. The analysis windows for on-treatment HCV RNA, vital signs and safety laboratory data are provided in [Table 3-1](#).

Table 3-1. Analysis Windows for On-treatment HCV RNA, Vital Signs and Safety Laboratory Data

Nominal Visit	Nominal Day	Lower Limit	Upper Limit
Baseline	1	(none)	1
Week 1	7	2	11
Week 2	14	12	21
Week 4	28	22	35
Week 6	42	36	49
Week 8	56	50	63
Week 10	70	64	77
Week 12	84	78	≥ 85

HCV RNA, vital sign, and safety laboratory data collected after the last dose date + 3 days will be assigned to the posttreatment follow-up (FU) visits. Visit windows will be calculated from the last dose date (ie, FU Day = collection date minus the last dose date) as shown in [Table 3-2](#).

Table 3-2. Analysis Windows for Posttreatment HCV RNA, Vital Signs and Safety Laboratory Data

Nominal FU ^a Visit	HCV RNA			Vital Signs and Safety Laboratory Data ^b		
	Nominal FU Day	Lower Limit	Upper Limit	Nominal FU Day	Lower Limit	Upper Limit
FU-4	28	21	69	28	4	30
FU-12	84	70	146	NA	NA	NA
FU-24	168	147	210	NA	NA	NA

a FU-x visit = posttreatment Week-x follow-up visit.

b Vital signs and safety labs will only be summarized for the FU-4 visit (up to 30 days after last dose).

ECG data collected up to the last dose date + 3 days are considered to be on-treatment data. Qualitative assessments of whether the ECG is normal or abnormal will be assessed for on-treatment data based on the visit windows as shown in [Table 3-3](#).

Table 3-3. Analysis Windows for On-treatment ECG Data

Nominal Visit	Nominal Day	Lower Limit	Upper Limit
Baseline	1	(none)	1
Week 1	7	2	45
Week 12	84	46	(none)

Note: ECGs are to be collected at screening, Day 1, Week 1, and Week 12 or End of Treatment. For purposes of analysis, baseline value will be the last available value prior to the first dose of study drug and end of treatment value will be the last available value on or prior to the last dose date + 3 days.

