6.2. Secondary Efficacy Endpoints

6.2.1. Definition of Secondary Efficacy Endpoints

Secondary efficacy endpoints include the following:

- The percentage of subjects with HCV RNA < LLOQ 4 and 24 weeks after discontinuation of treatment (SVR 4 and SVR 24)
- The percentage of subjects with HCV RNA < LLOQ while on treatment by study visit
- HCV RNA (\log_{10} IU/mL) and change from baseline in HCV RNA (\log_{10} IU/mL) through end of treatment (EOT)
- The percentage of subjects with virologic failure as the following:

On-treatment virologic failure

- HCV RNA \geq LLOQ after having previously had HCV RNA < LLOQ, while on treatment, confirmed with 2 consecutive values (note, second confirmation value can be posttreatment), or last available on-treatment measurement with no subsequent follow-up values (ie, breakthrough)
- 1 \log_{10} IU/mL increase in HCV RNA from nadir while on treatment, confirmed with 2 consecutive values (note, second confirmation value can be posttreatment), or last available on-treatment measurement with no subsequent follow-up values (ie, rebound)
- HCV RNA persistently \geq LLOQ through 8 weeks of treatment (ie, nonresponse)

Relapse

- HCV RNA \geq LLOQ during the posttreatment period having achieved HCV RNA < LLOQ at end of treatment, confirmed with 2 consecutive values or last available posttreatment measurement
- Characterization of HCV drug resistance substitutions at baseline, during, and after therapy with SOF/VEL

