6.2.2. Analysis Methods for Secondary Efficacy Endpoints

For analyses of HCV RNA < LLOQ by visit while on treatment and during the posttreatment (SVR) follow-up period, subjects will be assigned a value at each visit based on the analysis visit windows specified in Section 3.7.2. Missing values will be imputed based on the categorical imputation rules described in Section 3.4.1. The two-sided 95% exact confidence interval based on Clopper-Pearson method will be provided for the percentage of subjects with HCV RNA < LLOQ at each visit by region and genotype. The overall category for “HCV RNA < LLOQ” will be split into the following 2 subcategories: “< LLOQ TND” for subjects with target not detected and “< LLOQ detected” for subjects with < LLOQ detected in tabular displays.

Graphs for the percentage of subjects with HCV RNA < LLOQ over time during treatment will be displayed.

Summary statistics will be presented for absolute values and change from baseline in HCV RNA (\log_{10} IU/mL) by visit through EOT. Imputation rules described in Section 3.4.1 will be used to assign HCV RNA values for missing values at a visit that are bracketed by “< LLOQ TND” and/or “< LLOQ detected”. Otherwise, a missing = excluded analysis will be performed. Plots of the mean \pm SD and median (Q1, Q3) of absolute values and changes from baseline in HCV RNA through EOT will be presented.

For the SVR12 endpoint analysis, a summary table of the number and percentage of subjects with SVR12, virologic failure (VF), and Other by region and genotype will be created. All subjects who achieve SVR12 will be categorized as SVR12. Virologic failure will be descriptively summarized as “on-treatment virologic failure” and relapse (which will be broken down by study drug completed yes/no). Subjects who do not achieve SVR12 and do not meet criteria for VF will be categorized as “Other”. The denominator for relapse will be the number of subjects who had HCV RNA < LLOQ on their last observed on-treatment HCV RNA measurement; otherwise, the denominator will be the number of subjects in the FAS.

[figure not shown]
A concordance table between SVR12 and SVR24 will be provided by region and genotype. Subjects with both observed SVR12 and observed SVR24 data will be included for this analysis.

Drug resistant substitutions will be analyzed and presented as part of the Clinical Study Report.

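### An unconfirmed HCV RNA ≥ LLOQ at the last on-treatment sample, then < LLOQ, then posttreatment viraemia, meets no virologic-failure definition, and end of treatment is undefined for HCV RNA

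*SAP*

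**What the plan says.** SAP Section 6.2.1 gives three forms of on-treatment virologic failure and one of relapse.

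- **Breakthrough** is HCV RNA ≥ LLOQ after an earlier on-treatment value < LLOQ. **Rebound** is a rise of 1 log10 IU/mL from the on-treatment nadir. Each must be "confirmed with 2 consecutive values (note, second confirmation value can be posttreatment"). The only exception is an unconfirmed value that is the "last available on-treatment measurement with no subsequent follow-up values (ie, breakthrough"); rebound has the same exception.
- **Nonresponse** is HCV RNA persistently ≥ "LLOQ through 8 weeks of treatment (ie, nonresponse").
- **Relapse** is HCV RNA ≥ LLOQ "during the posttreatment period having achieved HCV RNA < LLOQ at end of treatment", shown by two consecutive values or by the last available posttreatment one.

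Section 6.2.2 sorts subjects into SVR12, virologic failure and a residual: "Subjects who do not achieve SVR12 and do not meet criteria for VF will be categorized as" Other. The relapse denominator is the subjects who "had HCV RNA < LLOQ on their last observed on-treatment HCV RNA measurement".

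Section 3.7.2 sets the boundary between periods. HCV RNA data "collected after the last dose date + 3 days are considered posttreatment data".

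**The concern.** The percentage of subjects with virologic failure is a named secondary endpoint, and the table in Section 6.2.2 is where a reader sees how the subjects without SVR12 divide. The definitions should therefore place a documented return of virus after suppression under virologic failure. For one sequence of results they do not. An isolated late on-treatment value ≥ LLOQ blocks relapse, because the subject was not < LLOQ at end of treatment. The < LLOQ value that follows then blocks breakthrough and rebound, because it removes both the confirmation and the exception for a last value with nothing after it.

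A related weakness is that Section 6.2.1 does not say which HCV RNA measurement represents end of treatment. Section 6.2.2 implies an answer through its denominator, but the definition itself is silent.

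**Working it through.** The plan gives no figure on this point, so there is none to reproduce. The check applies the rules of 6.2.1 literally to a result sequence and then sizes one subject.

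**Inputs.** LLOQ is 15 IU/mL and values below it are set to 14 (Section 3.6). On-treatment data run to last dose + 3 days (3.7.2). End of treatment is taken as the last on-treatment value, which is how the 6.2.2 denominator is built. Planned numbers are 360 overall and 260 in Region 1 (1.2).

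**Step 1: the sequence.** HCV RNA < LLOQ at Weeks 4 to 10; 20 IU/mL at Week 12, the last on-treatment sample; < LLOQ at posttreatment Week 4; ≥ LLOQ at posttreatment Week 12 and confirmed. The sequence can be observed: under note i to Appendix 1 all subjects attend posttreatment Week 4, and those < LLOQ there go on to later visits.

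| Rule | Met? | Reason |
|---|---|---|
| Breakthrough | No | The next value is < LLOQ, so there is no confirmation; follow-up values exist, so the exception is closed |
| Rebound | No | log10(20/14) = 0.155, below 1 |
| Nonresponse | No | Already < LLOQ before Week 8 |
| Relapse | No | The last on-treatment value was ≥ LLOQ |

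The result does not depend on the late value being small. At 100,000 IU/mL, log10(100000/14) = 3.85 passes the size test for rebound, but the value is still unconfirmed and followed by other values. Coding the rules and trying 20, 100, 1,000 and 100,000 IU/mL gave no virologic-failure category each time.

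**Step 2: controls.** Changing one element restores a category. With the last on-treatment value < LLOQ the subject is a relapse. With a last on-treatment value of 1,000 IU/mL, the subject meets breakthrough and rebound if the first posttreatment value is 100,000 IU/mL, and also if there is no follow-up.

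**Step 3: how far the gap extends.** Take three levels (14, 100 and 100,000 IU/mL) at the seven visits from Week 1 to Week 12, giving 3^7 = 2,187 on-treatment patterns. Follow each with posttreatment < LLOQ and then two values of 100,000 IU/mL. Of these, 192 met no failure rule, and all 192 had a last on-treatment value ≥ LLOQ. The hole is therefore single and systematic. The count is of logical patterns and says nothing about how often they occur.

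**Step 4: the table category.** The subject falls in Other only if SVR12 is missed, meaning the latest record in the posttreatment Week 12 window (Days 70 to 146; 3.7.2 and 3.7.3) is ≥ LLOQ. If that record is < LLOQ and virus returns only by posttreatment Week 24, the subject is tabulated as SVR12, though still under no failure definition.

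**Step 5: early stoppers.** Suppose a subject stops before completing 8 weeks with HCV RNA still falling but ≥ LLOQ (for example 1,000, 500 and 100 IU/mL at Weeks 1, 2 and 4). The first < LLOQ sample comes more than 3 days after the last dose, and the subject later becomes viraemic.
- If end of treatment is the last on-treatment value, no category fits.
- If it is the sample from the visit that Appendix 1 labels 12/ET, and that sample is < LLOQ, the subject is a relapse in the numerator but is outside the 6.2.2 denominator.

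**Step 6: size.** One subject is 1/360 = 0.28 percentage points overall and 1/260 = 0.38 points in Region 1.

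**The case against.** The strongest reply is that this is a rare edge case in a descriptive summary. No test of virologic failure is planned, the subject is still an SVR12 failure in the primary analysis when virus is back by the Week 12 window, and Section 3 promises by-subject listings in which the profile would be visible. All of that stands and limits the weight of the point. It does not supply a category for the sequence in Step 1, and nothing else in the SAP does.

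A second reply is that end of treatment could be read loosely, as the sample from the 12/ET visit. Section 3.7.2 ties an end-of-treatment value to last dose + 3 days only in its ECG note. The reply succeeds in part: the early stopper is unclassified on one reading only. It does not help the main case, where the Week 12 visit sample is itself ≥ LLOQ.

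A reader might go further in three ways that the SAP does not support.
- One might infer that the plan files drug failures as dropouts in the drug's favour. The omission can only lower the virologic-failure count, but Section 6.2.2 defines Other purely as a residual, and the primary endpoint gains nothing from it.
- One might express the effect as a share of all failures. That needs an expected number of failures, and the SAP gives none.
- One might read 192 of 2,187 as a rate. It is an unweighted grid.

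**Conclusion.** The gap is real. A subject who is suppressed on treatment, has one unconfirmed value ≥ LLOQ at the last on-treatment measurement, is < LLOQ at the first posttreatment measurement and is then viraemic meets no definition of virologic failure. If SVR12 is also missed, that subject is counted as Other. Separately, end of treatment for HCV RNA is undefined in 6.2.1 and needs to agree with the 6.2.2 denominator; whether some early stoppers are classified at all depends on it.

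The consequence is confined to the descriptive virologic-failure percentage and the split between virologic failure and Other. It is 0.28 points overall or 0.38 points in Region 1 for each such subject, assuming the planned numbers are analysed. The frequency is not given and is probably low. SVR12, its test and its power do not change. This is a minor point that is worth closing because the correction is cheap.

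**What to change.** 1. In 6.2.1, define end of treatment for HCV RNA as the last observed on-treatment measurement, with on-treatment as in 3.7.2.
2. In 6.2.1, extend relapse to HCV RNA ≥ LLOQ posttreatment, confirmed as now, after a value < LLOQ either at end of treatment or at a later posttreatment measurement, in subjects who do not meet on-treatment virologic failure.
3. In 6.2.2, make the relapse denominator all subjects without on-treatment virologic failure who have HCV RNA < LLOQ at the last on-treatment measurement or at any later posttreatment one, whatever happens next. Adding only those who recur would make entry to the denominator depend on the outcome.
4. The protocol is not at hand. If it carries the present definition, record the change in 6.4, which now declares none.

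The cost is a few lines of text and a small change to the derivation, with no new data. The virologic-failure count may rise slightly, and the definition would differ from the protocol's if the protocol uses the current wording.

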6.2.2. Analysis Methods for Secondary Efficacy Endpoints

For analyses of HCV RNA < LLOQ by visit while on treatment and during the posttreatment (SVR) follow-up period, subjects will be assigned a value at each visit based on the analysis visit windows specified in Section 3.7.2. Missing values will be imputed based on the categorical imputation rules described in Section 3.4.1. The two-sided 95% exact confidence interval based on Clopper-Pearson method will be provided for the percentage of subjects with HCV RNA < LLOQ at each visit by region and genotype. The overall category for “HCV RNA < LLOQ” will be split into the following 2 subcategories: “< LLOQ TND” for subjects with target not detected and “< LLOQ detected” for subjects with < LLOQ detected in tabular displays.

Graphs for the percentage of subjects with HCV RNA < LLOQ over time during treatment will be displayed.

Summary statistics will be presented for absolute values and change from baseline in HCV RNA (\log_{10} IU/mL) by visit through EOT. Imputation rules described in Section 3.4.1 will be used to assign HCV RNA values for missing values at a visit that are bracketed by “< LLOQ TND” and/or “< LLOQ detected”. Otherwise, a missing = excluded analysis will be performed. Plots of the mean \pm SD and median (Q1, Q3) of absolute values and changes from baseline in HCV RNA through EOT will be presented.

For the SVR12 endpoint analysis, a summary table of the number and percentage of subjects with SVR12, virologic failure (VF), and Other by region and genotype will be created. All subjects who achieve SVR12 will be categorized as SVR12. Virologic failure will be descriptively summarized as “on-treatment virologic failure” and relapse (which will be broken down by study drug completed yes/no). Subjects who do not achieve SVR12 and do not meet criteria for VF will be categorized as “Other”. The denominator for relapse will be the number of subjects who had HCV RNA < LLOQ on their last observed on-treatment HCV RNA measurement; otherwise, the denominator will be the number of subjects in the FAS.

[figure not shown]
A concordance table between SVR12 and SVR24 will be provided by region and genotype. Subjects with both observed SVR12 and observed SVR24 data will be included for this analysis.

Drug resistant substitutions will be analyzed and presented as part of the Clinical Study Report.

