1.2. Study Design

This is an international, multicenter, open-label study that will evaluate the safety, tolerability and antiviral efficacy of SOF/VEL for 12 weeks in treatment-naïve and treatment-experienced adults with chronic HCV infection. Subjects with or without cirrhosis will be enrolled.

Approximately 20% of subjects may be treatment experienced and approximately 20% of subjects may have compensated cirrhosis at screening.

Subjects with chronic HCV infection will be enrolled to receive SOF/VEL once daily for 12 weeks.

This multi-regional clinical trial (MRCT) is planned to be conducted in China, Malaysia, Singapore, Thailand, and Vietnam. China will be considered Region 1. Malaysia, Singapore, Thailand, and Vietnam, which are all located in Southeast Asia, will be considered Region 2.

Approximately 360 subjects will be enrolled in the study in total. The approximate number of subjects to be enrolled in each region according to HCV genotype is represented in the table below:

HCV GT (Prior Rx History)	GT-1 (TN, TE)	GT-2 (TN, TE)	GT-3 (TN, TE)	GT-4,5,6 (TN, TE)	Total
Region 1 (China)	80	60	60	60	260
Region 2 (Malaysia, Singapore, Thailand, Vietnam)	100				100

Rx = Treatment
 TN = Treatment Naïve, TE = Treatment Experienced

It is expected that a small number of subjects whose HCV genotype cannot be determined by the central laboratory (HCV genotype indeterminate) may also be enrolled.

The schedule of assessments is provided as an appendix to the SAP ([Appendix 1](#)).

The total time to complete all study visits is up to approximately 42 weeks including the following periods:

- 42-day (6-week) screening period
- 12-week treatment period
- Up to 24-week posttreatment period

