1.3. Sample Size and Power

The sample size justification is based on the Region 1 population. A sample size of 260 subjects in Region 1 will provide more than 80% power to detect an improvement of at least 6 percentage points in SVR12 rate from the performance goal of 85% by using a two-sided exact one-sample binomial test at the significance level of 0.05.

In addition, a confidence interval approach will be used to estimate the SVR12 rates for Region 2 and for the overall population (ie, combined Region 1 and Region 2). With 100 subjects from Region 2, and 360 subjects from the overall population, the 2-sided 95% exact CIs for different observed SVR12 rates are presented in the table below.

Region	Observed SVR12 rate	2-sided 95% exact CI
Region 2 (n=100)	80% (80 out of 100)	71% - 87%
	90% (90 out of 100)	82% - 95%
Overall (n=360)	80% (288 out of 360)	75% - 84%
	90% (324 out of 360)	86% - 93%

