4. SUBJECT DISPOSITION

4.1. Subject Enrollment and Disposition

A summary of subject enrollment will be provided for each investigator. The summary will present the number and percentage of subjects in the Safety Analysis Set. The denominator for the percentage calculation will be the total number of subjects analyzed.

A summary of subject disposition will be provided by region and genotype. This summary will present the number of subjects screened, the number of subjects enrolled, the number of subjects enrolled but never treated, and the number and percentage of subjects in each of the categories listed below. For the “Treated” category, the denominator for the percentage calculation will be the total number of subjects enrolled for each column. For all other categories, the denominator for the percentage calculation will be the total number of subjects in the Safety Analysis Set for each column.

- Treated (Safety Analysis Set)
- In FAS
- Continuing study treatment if applicable
- Completed study treatment
- Did not complete study treatment with reasons for premature discontinuation of study treatment
- Completed study
- Did not complete the study with reasons for premature discontinuation of study

Among subjects who completed study treatment and who discontinued study treatment, the number and percentage of subjects will be summarized for:

- Who had no HCV posttreatment Week 4 assessment and thereafter (No HCV FU-4 and thereafter)
- Who had HCV posttreatment Week 4 assessment but no HCV posttreatment Week 12 assessment and thereafter (With HCV FU-4 but No FU-12 and thereafter)

If a subject did not have any HCV RNA assessment ≥ 21 days after the last dose of any study drug (ie, lower bound of FU-4 visit for HCV RNA data), the subject is categorized as having “No HCV FU-4 and thereafter”. If a subject had the HCV FU-4 assessment but did not have any HCV RNA assessment ≥ 70 days after the last dose of any study drug (ie, lower bound of FU-12 visit for HCV RNA data), the subject is categorized as having “With HCV FU-4 but No FU-12 and thereafter”.

In addition, the total number of subjects who were enrolled, and the number of subjects in each of the disposition categories listed above will be depicted by a flowchart.

The following by-subject listings will be provided by region and subject ID number in ascending order to support the above summary tables:

- Disposition for subjects who complete study treatment and study

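### Does splitting relapse by treatment completion, with only one relapse denominator stated, hide the relapse rate in subjects who stopped early?

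*SAP*

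**What the plan says.** Section 6.2.2 plans a table of counts and percentages that places each subject under SVR12, virologic failure or Other, by region and genotype. Its treatment of failure is introduced with "Virologic failure will be descriptively summarized as", so no test is attached. Within failure, the SAP lists on-treatment failure and "relapse (which will be broken down by study drug completed yes/no").

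Two denominators are then given. For relapse: "The denominator for relapse will be the number of subjects who had HCV RNA < LLOQ on their last observed on-treatment HCV RNA measurement". For the rest: "otherwise, the denominator will be the number of subjects in the FAS". Nothing further is said about the completed and not-completed rows.

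The relapse definition in Section 6.2.1 requires prior suppression: "having achieved HCV RNA < LLOQ at end of treatment, confirmed with 2 consecutive values or last available posttreatment measurement". Section 4.1 separately tabulates, by region and genotype, subjects who finished treatment and those in the category "Did not complete study treatment with reasons for premature discontinuation of study treatment", and lists the latter individually.

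**The concern.** The SAP leaves the FAS for relapse because only a subject who was suppressed at the end of treatment can relapse. The same reasoning suggests that a row for early stoppers should be divided by suppressed early stoppers. Yet the stated denominator has no qualifier for completion status, and the word that sends everything else to the FAS seems to leave no third option.

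Read literally, the not-completed row would be divided by a group made up almost wholly of completers. A small early-stop group would then always show a tiny percentage. A reader could conclude that stopping early carries no more relapse than finishing when the data show the opposite. Two programmers could also read the sentence differently and print very different figures for the same row.

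**Working it through.** **The plan's own figures.** The SAP states no expected relapse rate, dropout rate or number of early stoppers, so there is no relapse figure to reproduce. Its one power statement (Section 1.3: "A sample size of 260 subjects in Region 1 will provide more than 80% power to detect an improvement of at least 6 percentage points") does reproduce. With N = 260, 85% against 91% and a two-sided exact test at 0.05, the upper rejection limit is 233/260 and power is 81.5%. The four exact intervals in that section also reproduce: 71-87%, 82-95%, 75-84% and 86-93%. None of these depends on relapse.

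**Notation.** Let R be all subjects with HCV RNA < LLOQ at the last observed on-treatment measurement, E those among them who stopped early, and r the relapses among E.

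- Pooled reading: early-stop row = r / R.
- Within-row reading: early-stop row = r / E.
- Ratio of the two = R / E, whatever r is.

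**Size, first set of assumed counts.** Take R = 360, an upper bound from Section 1.2 ("Approximately 360 subjects will be enrolled in the study in total"), and r = 2. The pooled figure is 2/360 = 0.56% throughout.

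| E (assumed) | Within-row | Ratio R/E |
|---|---|---|
| 4 | 2/4 = 50% | 90 |
| 8 | 2/8 = 25% | 45 |
| 18 | 2/18 = 11.1% | 20 |

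With 6 relapses among completers, that row is 6/360 = 1.67% pooled. Within row it lies between 6/356 = 1.69% and 6/342 = 1.75%, a change of less than 0.1 point.

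**Size, second set of assumed counts.** Take R = 355, with 345 completers (4 relapses) and 10 early stoppers (3 relapses).

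- Pooled: 4/355 = 1.1% and 3/355 = 0.8%.
- Within row: 4/345 = 1.2% (exact 95% CI 0.3-2.9) and 3/10 = 30.0% (6.7-65.2).
- Total relapse is 7/355 = 2.0% on either reading. The pooled rows add to it (4/355 + 3/355 = 7/355); the within-row rates do not.

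**Which reading does the text support?** The denominator sentence says who is at risk of relapse: subjects suppressed at their last on-treatment measurement. Applied to the table as a whole it gives R. Applied to the not-completed row it gives E. The sentence specifies neither. The FAS alternative is weak, because relapse has been given its own rule and the FAS is kept for the other categories. A figure follows that paragraph in the SAP but was not available here, so nothing is inferred from it.

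**What can a reader recover on the pooled reading?** The table prints r. Section 4.1 prints the number D who did not complete treatment, in the Safety Analysis Set, which is defined in the same terms as the FAS (Sections 3.1.2 and 3.1.3). Since E cannot exceed D, r/D is a lower bound for r/E. The exact E is not a planned summary row, but the by-subject listings provided for in Section 3 would allow it to be counted.

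**The case for a change.** The strongest case for a change is that an analysis plan should not leave a row denominator to the programmer. This SAP is explicit elsewhere: Section 4.1 separates the denominator for treated subjects from the others, and Sections 7.3.2.2 and 7.6 define theirs. Adding a qualifier for completion status means reading in words that Section 6.2.2 lacks. In the second example the order of the two rows reverses between readings. The non-completers in Section 4.1 include subjects who were never suppressed, so the exact rate cannot be taken from the planned summary tables. The remedy would be one sentence and no new data.

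Part of this stands. The row denominator is unstated, and the pooled percentage would not be a relapse rate among early stoppers. The rest does not carry the point to a change:

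- The SAP states no aim of comparing relapse risk by completion. Sub-rows on a common denominator that add to the total are an ordinary way to show where the relapses came from.
- Counts stand beside the percentages, so the early-stop relapses are not hidden.
- The counts that make the gap look striking are assumed. The ratio R/E only restates how small the early-stop group was taken to be.
- Within-row percentages would gain little in this table. It is laid out over three region groups and ten genotype groups (Section 3.2). With the 10 early stoppers of the second example spread over those columns, many cells would hold no subject or one, giving no percentage, 0% or 100%.

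**Conclusion.** No change is needed. Section 6.2.2 leaves the denominator of the two completion rows unspecified; it does not prescribe a wrong one. The at-risk rule it gives can be applied within each row, and an analyst preparing the table can do that, or print counts over row totals, without departing from the text.

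If the pooled group were used, the early-stop percentage would be smaller than the within-group rate by R/E: 20- to 90-fold for 18 to 4 early stoppers among 360 responders, figures that rest wholly on assumed counts. The completer row would move by less than 0.1 point in those cases. Total relapse, the SVR12 rates and intervals, and the Region 1 test with its 81.5% power are the same on either reading. The table is descriptive and secondary, and no planned conclusion depends on the split.
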